5.2.12 Safety Analyses

The incidence of hypoglycemia (total, nocturnal, and severe) and number of hypoglycemic episodes will be summarized. Summary tables providing frequency counts and the percentage of subjects within each category will be provided for Level 1 hypoglycemia (SMBG <70 mg/dL)

and Level 2 hypoglycemia (SMBG <54 mg/dL). Exposure-adjusted incidence rates and exposure-adjusted event rates will be calculated and summarized.

The number and percentage of subjects with TEAEs will be tabulated by system organ class and preferred term by relationship to treatment and by severity.

A summary table by study visit with descriptive statistics for FEV₁ at all time points will be provided. The FEV₁ data will also be presented graphically.

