Test Product, Dose, and Mode of Administration:	
Test product: AfreZZa® [insulin human] inhalation powder
 
Active ingredient: Human insulin, recombinant DNA origin
 
Dose regimen: Individualized
 
Mode of Administration: Oral inhalation

Basal Insulin Therapy Dose, and Mode of Administration:	
Basal insulin analog: The subject's personal basal insulin. The dose and type of basal insulin should not be changed between Visits 1 and 3.
 
Dose regimen: Individualized
 
Mode of Administration: Subcutaneous injection or via pump. Note: Pumps cannot be in automated insulin delivery mode for the 3 hours before or during Visits 2 and 3.

Duration of Treatment:	Two individual doses of AfreZZa will be administered during this study, during Visits 2 and 3, with a standardized meal challenge.
Criteria for Evaluation:	
This study will evaluate the efficacy and safety of AfreZZa administered according to new dosing guidelines, combined with basal insulin, based on the endpoints outlined below:
 
Efficacy Endpoint
 
 Change in SMBG from immediately before administering the dose of AfreZZa (t=0; baseline) to 15, 30, 45, 60, 90 and 120 minutes after AfreZZa dosing 
Safety Endpoints
 
 Event rates and incidence Level 1 (<70 mg/dL) and Level 2 (<54 mg/dL) hypoglycemic events Event rates and incidence of severe hypoglycemic events, defined as events requiring assistance of another person to actively administer carbohydrate, glucagon, or other resuscitative actions Incidence and severity of AEs: TEAEs, SAEs, and AESIs Change in FEV₁ from t=0 to 120 minutes after AfreZZa dosing
Statistical Methods:	
Sample Size Determination
 
Twenty subjects are planned to complete the study. Subjects who do not complete the study may be replaced. The sample size of 20 subjects was not determined using statistical methods, but rather was chosen based on clinical considerations.
 
Analysis Populations

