2.2 Secondary Objective

The secondary objective of this study is:

- To evaluate the safety of Afrezza administered at 2 different doses, combined with basal insulin, in adults 18 years and older with T1DM or T2DM, as measured by:
 - Event rates and incidence of Level 1 (<70 mg/dL) and Level 2 (<54 mg/dL) hypoglycemic events within the 120 minutes after Afrezza dosing
 - Event rates and incidence of severe hypoglycemic events, defined as events requiring assistance of another person to actively administer carbohydrate, glucagon, or other resuscitative actions within the 120 minutes after Afrezza dosing
 - Change in percent predicted forced expiratory volume in 1 second (FEV₁) from before Afrezza dosing to 120 minutes after Afrezza dosing
 - Incidence and severity of adverse events (AEs): treatment-emergent adverse events (TEAEs), serious AEs (SAEs), and AEs of special interest (AESIs)

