- e. Subjects should use their Sponsor-provided blood glucose meter to take SMBG values: 15 minutes before their AfreZZa dose, immediately before administering their dose of AfreZZa (t=0; baseline) and at 15, 30, 45, 60, 90 and 120 minutes after AfreZZa dosing. Additional SMBG measurements may be taken per Investigator discretion.
- f. If the subject is wearing a CGM, they will be asked to write down their CGM value every time they take an SMBG measurement in the clinic. These CGM values will be entered in the CRF completed at Visit 2 and Visit 3.
- g. At the beginning of Visits 2 and 3, before their dose of AfreZZa, subjects will have FEV₁ measurements taken in the clinic. After completion of the standardized meal challenge (120 minutes after AfreZZa dose), subjects will have another FEV₁ measurement before leaving the clinic.
- h. Any AE that occurs after the subject enrolls in the study (consent date) will be recorded.
- i. Hypoglycemic episodes will be defined as all SMBG measurements <70 mg/dL. See Section [3.5.5.6](#).

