The Afrezza dose to be taken at Visit 3 will be based on the dose of RAA that the subject would normally take, converted by multiplying their RAA dose by 2 and rounding down to the nearest Afrezza cartridge size as shown in [Table 4](#). If the subject's normal RAA dose is <4 units, the subject will be asked to consume enough nutritional shake, per their normal insulin:carbohydrate ratio, to cover an RAA dose of ≥ 4 units such that their Afrezza dose at Visit 3 is higher than the dose taken at Visit 2.

For Afrezza doses exceeding 12 units, inhalations from multiple cartridges are necessary. To achieve the required total mealtime dose, subjects should use a combination of 4-unit, 8-unit, and 12-unit cartridges.

Table 4: Dose of AfreZZa at Visit 3

RAA Dose (Units)	AfreZZa Dose (Units)
<4	4
4	8
5	
6	12
7	
8	16
9	
10	20
11	
12	24
13	
14	28
15	
16	32
17	
18	36
19	
20	40
21	
22	44
23	
24	48

RAA=rapid-acting insulin analog (e.g., insulin aspart or insulin lispro)

Note: There is no maximum dose of AfreZZa and the required total mealtime dose may differ from the examples provided in this table.

The dose of AfreZZa will be administered at the start of the meal challenge. The subject must consume 1 to 2 bottles of nutritional shake within 15 minutes for the meal challenge and take SMBG measurements 15 minutes before their AfreZZa dose, immediately before administering the AfreZZa dose (t=0; baseline) and at 15, 30, 45, 60, 90, and 120 minutes after AfreZZa dosing. The subject will remain under clinical supervision for the 2 hours after their dose of AfreZZa.

If the subject is wearing a CGM, they will be asked to write down their CGM value every time they take an SMBG measurement in the clinic. These CGM values will be entered in the CRF completed at Visit 3.

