3.5.4 Efficacy Assessment

3.5.4.1 Self-Monitored Blood Glucose

Subjects will measure their blood glucose using the Sponsor-provided blood glucose meter and corresponding supplies (lancets, control solutions, test strips, etc.). Subjects will be instructed at both Visits 2 and 3 to take SMBG values 15 minutes before their AfreZZa dose, immediately before administering their dose of AfreZZa (t=0; baseline), and at 30, 45, 60, 90 and 120 minutes after AfreZZa dosing. Additional SMBG measurements may be taken per Investigator discretion.

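### Section 5.2.12 plans hypoglycaemia summaries without the objective's 120-minute window and adds a nocturnal category that no scheduled measurement supports

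*Combined protocol and SAP*

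**What the plan says.** The secondary objective (section 2.2 and the synopsis) measures Level 1, Level 2 and severe events inside a fixed window; section 2.2 refers to "hypoglycemic events within the 120 minutes after Afrezza dosing".

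Three places omit that window:
- The synopsis endpoint list gives "Event rates and incidence Level 1 (<70 mg/dL) and Level 2 (<54 mg/dL) hypoglycemic events" and stops there.
- Section 5.2.12 says "The incidence of hypoglycemia (total, nocturnal, and severe) and number of hypoglycemic episodes will be summarized", and then "Exposure-adjusted incidence rates and exposure-adjusted event rates will be calculated and summarized".
- The synopsis paragraph on analysis of safety endpoints makes the same plan as 5.2.12.

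Neither nocturnal nor exposure is defined anywhere in the document.

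On collection, Table 2 footnote i says "Hypoglycemic episodes will be defined as all SMBG measurements <70 mg/dL". Section 3.5.4.1 says "Subjects will be instructed at both Visits 2 and 3 to take SMBG values 15 minutes before their AfreZZa dose" and continues with post-dose times up to 120 minutes. For continuous glucose monitor users, footnote f says "they will be asked to write down their CGM value every time they take an SMBG measurement in the clinic". On the length of stay, the dosing sections for Visits 2 and 3 say "The subject will remain under clinical supervision for the 2 hours after their dose of AfreZZa"; the synopsis makes 2 hours a minimum.

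Section 3.5.5.6 keeps nonsevere episodes off the adverse event page and sends them to the hypoglycaemia page of the CRF. It classes severe events as SAEs.

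**The concern.** The objective defines one endpoint and the analysis text describes a wider one that the visit schedule was not built to observe. A nocturnal row would be filled, if at all, by events that nobody is scheduled to measure or ask about. An empty row could then be read as evidence of safety overnight after inhaled insulin, including after the higher dose, when it shows only that nothing was collected.

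Unwindowed counts raise a second difficulty. The recording item at Visit 3 might be used to enter episodes that occurred at home after Visit 2. Visit 4 has no such item, so the two doses would not be followed in the same way after discharge.

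The rates also need a denominator. Without the window, two analysts could choose very different person-time and both comply with the text.

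**Working it through.** The plan gives no figure to reproduce on this point, and its sample size of 20 has no statistical basis (section 5.2.3). The check compares sections and then applies simple arithmetic.

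**1. Scheduled readings.** Table 2 footnote e and the dosing sections for Visits 2 and 3 list -15, 0, 15, 30, 45, 60, 90 and 120 minutes: 8 per visit.
- A subject attending both treatment visits has 8 x 2 = 16; a subject who stops after Visit 2 has 8.
- Section 3.5.4.1 omits the 15-minute reading, which gives 7 per visit. This does not change the argument.
- None of these readings is at home, and none is at night if visits are in the daytime (assumption).
- Beyond these, the document provides for additional readings at the Investigator's discretion, a repeat after carbohydrate when the pre-dose value is low, and repeats every 15 minutes until a hypoglycaemic episode resolves (3.5.5.6). None of these schedules overnight measurement.

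**2. Scheduled recording.**

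| Item | Visit 2 | Visit 3 | Visit 4 / Early Termination |
|---|---|---|---|
| Hypoglycaemia recording | yes | yes | no |
| Glucose meter review | yes | yes | no |
| Adverse events | yes | yes | yes |

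The source is Table 2, confirmed by the procedure lists for each visit. Nonsevere episodes are not adverse events under 3.5.5.6, so the last row does not cover them.

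**3. Coverage after the last dose.** Visit 4 falls 24 to 72 hours after the last dose (synopsis and section 3.1), and the minimum stay is 2 hours.
- Share with scheduled recording: 2/72 = 2.8% to 2/24 = 8.3%.
- Remaining time: 24 - 2 = 22 hours to 72 - 2 = 70 hours per subject.
- Nights, with daytime visits: 1 to 3 per subject, or 20 x 1 = 20 to 20 x 3 = 60 subject-nights for 20 completers.

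For a subject who does not proceed to Visit 3, this interval starts at the Visit 2 dose.

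**4. Possible difference between doses.** Between Visits 2 and 3 there are 1 to 5 nights (Day 1 to Day 4, plus or minus 2 days). Table 2 does not say whether the Visit 3 recording item looks back over them. If it does, nonsevere home events after the Visit 2 dose would be solicited, and those after the Visit 3 dose would not. If it does not, neither dose has solicited follow-up after discharge.

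**5. Exposure.** Assume 20 subjects receive both doses.
- Windowed: 20 x 2 doses x 2 h = 80 person-hours.
- First dose to Visit 4 (Day 1 to Day 7, 6 days): 20 x 6 = 120 person-days = 2,880 person-hours.
- Ratio: 2,880/80 = 36. With Visit 4 on Day 5 or Day 9, it is (20 x 4 x 24)/80 = 24 or (20 x 8 x 24)/80 = 48.

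The same event count can therefore give rates that differ 24- to 48-fold. With 2 observed hours per dose received, each dose has 20 x 2 = 40 subject-hours, so one event is 100/40 = 2.5 per 100 subject-hours. If only 15 subjects receive the Visit 3 dose (assumption; proceeding is the Investigator's decision), that dose has 15 x 2 = 30 subject-hours and one event is 100/30 = 3.3 per 100.

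**The case against.** The strongest reply is that the objective already defines the endpoint. On that view 5.2.12 merely fails to repeat the window, total means all levels within it, and collection matches it. Much of this stands. Not soliciting nonsevere episodes after discharge is consistent with a 120-minute objective and is not in itself a defect. A total table would still hold every in-clinic episode. The reply does not rescue nocturnal, which has no sensible meaning inside the 2 hours after a supervised, presumably daytime, meal challenge.

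A reader might also infer that a nonsevere episode after the last discharge cannot reach the database. The documents do not support that. Section 3.5.5.6 sets no visit limit on the hypoglycaemia page, and section 6.4.1 allows the CRFs of a subject leaving the study to be completed at the final visit or shortly afterwards. An episode volunteered at Visit 4 could be entered. What is missing is any scheduled step that asks for it. The discharge instructions, CRF pages and site operations manual cannot be seen here and may add to this.

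Finally, reading the nocturnal row as a result for the higher dose needs a split by dose. Section 5.2.12 specifies a by-visit table for FEV₁ but not for hypoglycaemia.

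**Conclusion.** The analysis text is wider than both the objective and the scheduled data. A nocturnal incidence near zero would be uninformative, because 1 to 3 nights per subject after the last dose have no scheduled measurement and no solicited recording of nonsevere episodes. This assumes daytime visits. How many such episodes would occur cannot be estimated from the documents.

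Two stronger readings should be avoided. One is that the comparison of doses on hypoglycaemia is biased. The 0-120 minute endpoint is observed in the same way at both visits; an imbalance arises only for unwindowed counts, and only if Visit 3 recording reaches back to the period since Visit 2, which the text leaves open. The other is that severe hypoglycaemia is missed. Severe events are SAEs under 3.5.5.6 and 4.2.1, and adverse events are recorded at Visit 4.

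The undefined exposure term alone would be missing detail; it matters here because the omitted window permits very different denominators. Severity is minor: the effect is confined to descriptive safety tables, and no test, sample size or decision rule depends on it.

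**What to change.** 1. In 5.2.12 and the synopsis, make a 0-120 minute table, by visit and dose, the analysis of the secondary endpoint. Define exposure as 2 observed hours per dose received.
2. List all other captured events separately: in-clinic episodes after 120 minutes, any post-discharge episodes, and all severe events whenever they occur. Restricting the whole hypoglycaemia analysis to 120 minutes would drop events that the study does capture.
3. Delete nocturnal. Alternatively, define and keep it only if hypoglycaemia recording and meter review are added at Visit 4/Early Termination in Table 2 and section 3.5.2.3, with results reported descriptively by most recent dose. In that case, also state whether recording at Visit 3 covers the period since Visit 2.

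Items 1 and 2, with deletion of nocturnal, cost only wording and table shells. The alternative in item 3 adds two entries at a visit that already takes place. Its drawback is that post-discharge events would rest on unscheduled readings and self-report, would be incomplete, and would be only weakly attributable to one dose in subjects who continue their own basal insulin.

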The AfreZZa dose to be taken at Visit 2 will be based on the dose of RAA that the subject would normally take, converted according to the guidelines provided in the current AfreZZa PI as shown in Table 3.

For AfreZZa doses exceeding 12 units, inhalations from multiple cartridges are necessary. To achieve the required total mealtime dose, subjects should use a combination of 4-unit, 8-unit, and 12-unit cartridges.

Table 3: Dose of AfreZZa at Visit 2

RAA Dose (Units)	AfreZZa Dose (Units)
Up to 4	4
5	8
6	
7	
8	
9	12
10	
11	
12	
13	16
14	
15	
16	
17	20
18	
19	
20	
21	24
22	
23	
24	

RAA=rapid-acting insulin analog (e.g., insulin aspart or insulin lispro)

Note: There is no maximum dose of AfreZZa and the required total mealtime dose may differ from the examples provided in this table.

The dose of AfreZZa will be administered at the start of the meal challenge. The subject must consume 1 to 2 bottles of nutritional shake within 15 minutes for the meal challenge and take SMBG measurements 15 minutes before their AfreZZa dose, immediately before administering the AfreZZa dose ($t=0$; baseline) and at 15, 30, 45, 60, 90, and 120 minutes after AfreZZa dosing. The subject will remain under clinical supervision for the 2 hours after their dose of AfreZZa.

If the subject is wearing a continuous glucose monitor (CGM), they will be asked to write down their CGM value every time they take an SMBG measurement in the clinic. These CGM values will be entered in the CRF completed at Visit 2.

After completing the standardized meal challenge, the Investigator will decide, based on the subject's glucose excursion at Visit 2 if the subject should proceed to Visit 3 where a titrated dose of AfreZZa will be administered according to [Table 4](#).

3.5.2.2.2 Visit 3

The following procedures will be performed at Visit 3:

- Record concomitant medications (see Section [3.4.7.2](#))
- Complete refresher training on the Afrezza inhaler using BluHale PRO
- Measure and record FEV₁ before Afrezza dose
- Take the dose of Afrezza with standardized meal challenge according to Section [3.5.2.2.1.1](#)
- Measure and record FEV₁ after completion of the meal challenge
- Record AEs
- Collect and review glucose meter data
- Record any hypoglycemic episodes (see Section [3.5.5.6](#))
- Provide discharge instructions to the subject

3.5.2.2.2.1 Standardized Meal Challenge and Afrezza Dosing at Visit 3

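### The TEAE table and the hypoglycemia summaries name no split by visit or dose, so they cannot show which of the two doses an event followed

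*Combined protocol and SAP*

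**What the plan says.** Section 2.2 sets the secondary objective: "To evaluate the safety of Afrezza administered at 2 different doses, combined with basal insulin". Its measures are Level 1, Level 2 and severe hypoglycemia in the 120 minutes after dosing, change in percent predicted FEV₁, and incidence and severity of TEAEs, SAEs and AESIs.

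Section 5.2.12 plans the safety summaries:

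- TEAEs: "The number and percentage of subjects with TEAEs will be tabulated by system organ class and preferred term", broken down by relationship and severity. No separate SAE or AESI table is described.
- Hypoglycemia: "The incidence of hypoglycemia (total, nocturnal, and severe) and number of hypoglycemic episodes will be summarized". Level 1 and Level 2 events get counts and percentages, and exposure-adjusted rates are promised. No visit or dose is named.
- Lung function: "A summary table by study visit with descriptive statistics for" FEV₁ at every time point.

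Section 5.2.4 defines one analysis population: everyone who receives a dose. Sections 3.1 and 3.5.2.2.1.1 have the Investigator decide, from the Visit 2 glucose excursion, "if the subject should proceed to Visit 3".

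**The concern.** The trial exists to set a label-based dose beside a second dose derived by a different rule, and safety is half of that comparison. A table of subjects with events that is not divided by dose carries no information on the contrast. Where the plan wants a by-visit presentation it says so, which makes the omission for adverse events and hypoglycemia stand out.

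Two things are at stake. The first is attribution: whether an event followed the Visit 2 or the Visit 3 dose. The second is the denominator: subjects who stop after Visit 2 stay in the analysis population but were never exposed to the second dose. If the split, its denominators and its attribution rule are not written down, they may be chosen after open-label data have been seen.

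**Working it through.** The plan has no calculated figure to reproduce. The 20 completers are stated in Section 5.2.3 not to rest on statistical methods, and no adverse event rate is given. All event counts and risks below are therefore assumptions.

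**1. Planned summaries side by side**

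| Summary | Section | Split named |
|---|---|---|
| Insulin dosing | 5.2.10 | by visit |
| SMBG | 5.2.11 | by visit |
| FEV₁ | 5.2.12 | by study visit |
| TEAEs | 5.2.12 | class, term, relationship, severity |
| Hypoglycemia | 5.2.12 | type and level only |

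Nonsevere hypoglycemia is kept off the adverse event page (Section 3.5.5.6), so splitting the TEAE table alone would leave Level 1 and Level 2 events undivided.

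**2. Attribution.** Assume 20 subjects, all dosed twice, 4 with an event after one dose only. The undivided table shows 4/20 = 20%. By visit, with exact (Clopper-Pearson) 95% intervals, this could be:

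- 0/20 (0 to 17%) versus 4/20 (6 to 44%)
- 2/20 (1 to 32%) versus 2/20 (1 to 32%)
- 4/20 (6 to 44%) versus 0/20 (0 to 17%)

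One published figure covers opposite dose patterns.

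**3. Denominator.** Assume 20 dosed at Visit 2, 15 at Visit 3, and events in 0 and then 3 subjects. By dose: 0/20 = 0% and 3/15 = 20%. Over everyone dosed: 3/20 = 15%. If all 20 proceed, the second-dose figure and the overall figure are both 3/20 = 15%.

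**4. Does an undivided percentage understate the second-dose risk in general?** Let p1 and p2 be the risks after each dose, independent within subject, and f the fraction proceeding to Visit 3, unrelated to risk. The percentage of subjects with any event is

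p1 + f(1 − p1)p2.

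It equals p2 when f = (p2 − p1) / [p2(1 − p1)].

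| p1 / p2 | 20 of 20 proceed | 15 | 10 | 5 | Equal to p2 at |
|---|---|---|---|---|---|
| 5% / 20% | 24.0% | 19.3% | 14.5% | 9.8% | 0.15/0.19 = 0.789, or 15.8 of 20 |
| 10% / 30% | 37.0% | 30.2% | 23.5% | 16.8% | 0.20/0.27 = 0.741, or 14.8 of 20 |
| 0% / 20% | 20.0% | 15.0% | 10.0% | 5.0% | 1.000, or 20 of 20 |

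With f = 1 the overall percentage is never below p2. Understatement needs drop-off: 15 or fewer proceeding in the first row, 14 or fewer in the second, any shortfall in the third.

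A rate per dose given behaves differently. With 5% / 20% and all proceeding it is (20 × 0.05 + 20 × 0.20)/40 = 12.5%. This applies only if exposure is counted in doses. The documents do not define the exposure unit and promise no such rate explicitly for TEAEs.

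**5. Can the split be derived?** Largely. Sections 4 and 4.2.1 record adverse event dates, and Section 5.2.10 lists drug administration by subject. Neither adverse event section names a clock time, so an event on the day of Visit 3 may not be placeable before or after the dose. No rule assigns events that fall between visits or after Visit 3.

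**6. Is Visit 3 always a different dose?** For an RAA dose of 5 units, Table 3 gives 8 units. The Visit 3 rule gives 2 × 5 = 10, rounded down to 8, as in Table 4. The two visits then have the same dose.

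**The case against.** The strongest reply is that the text is silent. It does not say that events are pooled, and the tables might be produced by visit anyway. Section 5.2.1 sorts individual listings by treatment, subject, visit and time point. With about 20 subjects and two supervised doses, a reader could place most events by hand. Section 3.4.3 says all subjects receive Afrezza at both visits, and completion under Section 3.3.3 requires the treatment visits, so the two denominators may turn out equal. The study is small and not randomised, so a formal safety contrast was never on offer.

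Much of this stands. A reader might infer that the plan prescribes pooling, that the secondary objective goes unanswered, or that the risk at the second dose is diluted. The documents do not support any of these as a general statement. Pooling is an inference from silence. FEV₁, one of the safety measures, is summarised by visit. Step 4 shows that dilution of a percentage of subjects depends on how many fail to reach Visit 3.

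The rest does not remove the point. A listing gives neither an incidence nor a denominator, and sorting by treatment may not separate doses when every subject receives the same product in a single arm. Subjects stopped after Visit 2 stay in the analysis population even if 20 others complete.

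**Conclusion.** The point holds in a limited form. Section 5.2.12 names no visit or dose split for TEAEs or hypoglycemia, and describes no separate SAE or AESI table. Followed as written, those summaries cannot show which dose events followed. This needs no assumption about event rates.

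The denominator problem is conditional on some subjects not proceeding to Visit 3, which the Investigator's decision makes possible but not certain. Its size then depends on the drop-off and the assumed risks. At 5% / 20%, the overall figure goes from 24.0% with all 20 proceeding to 14.5% with 10. These values assume independence within subject and progression unrelated to risk.

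A by-dose table would still be descriptive: the order is fixed, Visit 3 subjects are selected on their Visit 2 excursion, and there are about 20 completers. The change is worth making because it is cheap and lets the plan address its own objective.

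**What to change.** In Section 5.2.12, and in the matching synopsis text, state that:

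- TEAEs, SAEs, AESIs and Level 1, Level 2 and severe hypoglycemia are tabulated by most recent dose received before onset, with an added any-dose column.
- The denominator for each dose column is the number of subjects given that dose. For the any-dose column it is everyone dosed.
- The Visit 2 window runs from that dose to the Visit 3 dose, or to study exit for subjects with no Visit 3 dose. The Visit 3 window runs from that dose to study exit.
- Hypoglycemia tables use the 120 minutes after each dose, as in Section 2.2. A later severe event still appears in the SAE table, because Section 3.5.5.6 documents it as an SAE.
- Events on the day of Visit 3 are assigned by recorded onset time relative to the dose, or by a default stated in advance if no time is recorded.
- The comparison between columns is descriptive.

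Separately, the dosing rules in Tables 3 and 4 must be reconciled with the two-dose objective for an RAA dose of 5 units. Until then the columns are better labelled by visit than as lower and higher dose.

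The cost is one extra set of columns and a short attribution rule, plus an onset-time field on the adverse event page if it has none. No extra visits or subjects are needed.

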3.5.5.5 Pulmonary Function Tests

Subjects will undergo pulmonary function tests (spirometry) according to American Thoracic Society and European Respiratory Society recommendations in the clinic.

The FEV₁ values will be recorded in the CRF.

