5.2.1 General Considerations

All statistical processing will be performed using the most current version of SAS® software (SAS Institute Inc, Cary, NC) at the time of the analysis. Summary tables (descriptive statistics and/or frequency tables) will be provided for screening and/or baseline variables, efficacy variables, and safety variables. Continuous variables will be described by descriptive statistics (n, mean, median, standard deviation, minimum, and maximum). Frequency counts and percentage of subjects within each category will be provided for categorical data.

Individual data will be listed and sorted by treatment, subject identification number, visit, and time point.

Database lock will occur upon the completion of the study.

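### The stated FEV₁ analysis tabulates values at each time point, while the secondary objective is change in percent predicted FEV₁; the spread and extremes of that change are never summarised

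*Combined protocol and SAP*

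**What the plan says.** The protocol describes the pulmonary safety measure in three ways.

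- **Objective** (Section 2.2, and the synopsis objectives): "Change in percent predicted forced expiratory volume in 1 second (FEV₁) from before Afrezza dosing to 120 minutes after Afrezza dosing".
- **Endpoint** (synopsis, Criteria for Evaluation, Safety Endpoints): "Change in FEV₁ from t=0 to 120 minutes after AfreZZa dosing". Percent predicted is not mentioned.
- **Analysis** (Section 5.2.12, repeated in the synopsis under Statistical Methods): "A summary table by study visit with descriptive statistics for FEV₁ at all time points will be provided". A graph is also promised. Neither change nor percent predicted is mentioned.

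On data capture, Section 3.5.5.5 says "The FEV₁ values will be recorded in the CRF" and names no reference equation. Footnote g of Table 2 (Section 3.5.1) places the pre-dose FEV₁ at the start of Visits 2 and 3 and the second measurement 120 minutes after the dose.

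The general rules in Section 5.2.1 are "Summary tables (descriptive statistics and/or frequency tables) will be provided for screening and/or baseline variables, efficacy variables, and safety variables" and "Individual data will be listed and sorted by treatment, subject identification number, visit, and time point".

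**The concern.** The objective is about how much each subject's lung function moves after an inhaled dose. The stated table describes the group at each time point separately. These are different quantities, and the second does not determine the first.

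What is at stake is mostly the individual response. Section 4.1.3 makes a decline of more than 20% from baseline percent predicted FEV₁ an adverse event of special interest only when respiratory symptoms accompany it. A large fall without symptoms does not meet that definition, and the by-time-point table would not reveal it. It would be left to the subject listings, or possibly to a graph whose form is not described.

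The two treatment visits may also cover different people. After Visit 2 the investigator decides, from the glucose excursion, who goes on to Visit 3 (Sections 3.1 and 3.5.2.2.1.1), while everyone who receives a dose is analysed (Section 5.2.4). Visit 2 and Visit 3 columns then need not describe the same subjects.

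**Working it through.** There is no figure in the plan to reproduce. Section 5.2.3 says that the 20 completers were not derived statistically, and no SD, correlation or effect size for FEV₁ is given. The check is therefore what the planned table can and cannot yield.

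**1. Mean change in FEV₁: recoverable.** If the same n subjects have both values, mean(post) − mean(pre) = mean(post − pre). Between-subject spread does not enter.

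**2. SD of the change: not recoverable.** With equal SDs at the two times and pre/post correlation r,

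SD of change = SD × √(2(1 − r)).

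Section 5.2.1 fixes the reported statistics as n, mean, median, SD, minimum and maximum, so r is not reported. Taking assumed between-subject SDs of 10 to 20 percent-predicted points and r of 0.80 to 0.98 (neither is in the documents):

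| Assumed SD | Assumed r | SD of change |
|---|---|---|
| 10 | 0.98 | 10 × √0.04 = 2.0 |
| 15 | 0.90 | 15 × √0.20 = 6.7 |
| 20 | 0.80 | 20 × √0.40 = 12.6 |

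**3. Median and extremes of the change: not recoverable.** Constructed example, in percent-predicted points: 20 pre-dose values equally spaced from 75 to 115 (mean 95.0).

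- Set A: every subject falls by 2.0.
- Set B: the same 20 post-dose values, but with those of the 11th and 20th subjects exchanged.

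| | Set A | Set B |
|---|---|---|
| Post-dose mean | 93.0 | 93.0 |
| Post-dose SD | 12.45 | 12.45 |
| Post-dose median | 93.0 | 93.0 |
| Post-dose minimum, maximum | 73, 113 | 73, 113 |
| Mean change (93.0 − 95.0) | −2.0 | −2.0 |
| SD of change | 0 | 6.15 |
| Range of change | −2.0 to −2.0 | −20.9 to +16.9 |

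The planned table is identical for both. In Set B the largest fall is 20.9 points from 115, or 18.2% of that subject's pre-dose value, and nothing in the table points to it.

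**4. Percent predicted: not recoverable from FEV₁ means.** A subject's change in percent predicted is 100 × (post − pre) / predicted, and the predicted value differs between subjects. The mean of these ratios does not follow from mean FEV₁ in litres.

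**5. Timing of the baseline.** The endpoint counts from t=0, which the protocol defines as immediately before dosing. The pre-dose FEV₁ is taken at the beginning of the visit, as footnote g states. The objective's wording fits that measurement; the endpoint's does not quite.

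**The case against.** The best defence is that this is only wording. Change in FEV₁ is a listed safety endpoint, and Section 5.2.1 promises summary tables for safety variables and listings by subject, visit and time point. On a generous reading the change is covered, and any subject's fall can be worked out from the listing. The case report form is not among the documents, so percent predicted may well be recorded; the Section 4.1.3 rule already depends on it. All this is fair, and it means that no data are lost. But the general rule defines no change variable, and a listing is not a summary. Where Section 5.2.12 becomes specific, it specifies something else.

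Several stronger conclusions that a reader might infer do not stand:

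- *The table would hide a mean decline.* It would not. Step 1 shows that the mean change survives whenever pairs are complete. Pairs should mostly be complete, because the 120-minute test is done in clinic before the subject leaves, and n is reported.
- *Precision is lost because the columns would be compared as independent samples.* The plan contains no confidence interval, test or two-sample comparison, so there is no such analysis to criticise.
- *The question is sharper because Visit 3 doubles the labelled conversion.* Comparing Tables 3 and 4 for usual doses of 4 to 24 units, the Visit 3 to Visit 2 ratio runs from 1.0 (5 units: 8 against 8) to 2.0, with an unweighted average of about 1.7.

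**Conclusion.** The mismatch is real and limited. Followed as written, the plan reports mean FEV₁ at each time point, from which the mean change in FEV₁ can be obtained by subtraction when pairs are complete. It does not report the SD, median, minimum or maximum of the within-subject change, and it does not report percent predicted, the metric that its objective names. The endpoint list adds a third version with a slightly different baseline.

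The identity in step 1 and the example in step 3 need no clinical assumption. The range of 2.0 to 12.6 points for the SD of change rests on assumed SDs and correlations and shows only how much the table leaves open. A reader might take the mismatch to mean that the study cannot deliver its pulmonary endpoint. The documents do not support that: the paired FEV₁ measurements, age, height and gender are all collected. This is a gap in the specification that costs almost nothing to close.

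**What to change.** Add to Section 5.2.12 and to the matching synopsis text:

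> Within-subject change in percent predicted FEV₁ (and in FEV₁) from the same-visit pre-dose measurement to 120 minutes will be summarised by visit with n, mean, SD, median, minimum and maximum. The paired Visit 3 minus Visit 2 difference in this change will be given for subjects with both visits.

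Then:

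- Name the reference equation for percent predicted FEV₁, and say whether percent predicted is recorded on the case report form or derived. If it is derived using gender, say how a declined answer is handled, since Section 3.5.5.1 allows one.
- Align the synopsis endpoint with Section 2.2: percent predicted, measured from the pre-dose test at the start of the visit and not from t=0.

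A 95% confidence interval and the change to Visit 4 would be reasonable additions, but no objective requires them.

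Cost: a few lines of text, a derived change variable and a stated equation. No new visit or procedure is needed. Section 5.2 already provides for documenting changes to the analyses before database lock.
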